12.1 Participant Disposition

The number and percentage of participants screened, enrolled, and randomised in the study will be presented, together with the number and percentage of participants included in each analysis set. The number of screen failures and participants enrolled but not randomised will also be presented. Reasons for exclusion from each analysis set will not be tabulated but will be listed.

Reason for screen failure, including inclusion and exclusion criteria not met, will be listed.

The participant disposition for the study including the number and percentage of participants who completed the study, withdrew from the study prematurely, and a breakdown of the corresponding reasons for withdrawal will be summarised using the Intent-to treat analysis set. In addition, the number and percentage of participants completing the vaccine regimen and discontinuing the vaccine regimen along with a breakdown of the corresponding reasons for discontinuation will be summarised. Listings of end of study and end of treatment status will be presented for all randomised participants.

A tabulation of the number and percentage of participants screened, enrolled, and randomised to each treatment group in each country and centre will be presented using all screened participants.

12.2 Protocol Deviations

The study specific Protocol Deviation Guidance Document defines all important protocol deviations.

Per PRA processes, important protocol deviations data will be entered into our system of record (PSO). The study team and the Sponsor will conduct on-going reviews of the deviation data from PSO and the resulting set of evaluable participants throughout the study, adjusting the deviation criteria as seems appropriate.

Protocol deviations will be classified into major (important) or minor (non-important) deviations. Protocol deviations leading to a participant's exclusion from the Per-protocol analysis set and Immunogenicity analysis set will be reviewed based on their possible impact on the study results in a data review meeting prior to database lock. The Per-protocol analysis set and Immunogenicity analysis set must be finalised at the post-freeze data review meeting (or earlier) prior to database lock.

A summary of the number and percentage of protocol deviations by deviation type (major, minor) and category will be provided using the Intent-to-treat analysis set. In addition, a by-participant listing of all protocol deviations will be presented.

12.3 Demographic and Baseline Characteristics

All demographic and baseline characteristics analyses will use the Intent-to-treat analysis set unless otherwise stated.

Frequency distributions and summary statistics for demographics and baseline characteristics including sex, race, ethnicity, age at informed consent (years), age group (18-64 years, ≥ 65 years), height (cm), weight (kg), and BMI (kg/m^2) will be summarised using the Intent-to-treat analysis set and additionally the Per-protocol analysis set and Immunogenicity analysis set. Date of informed consent and randomisation will be listed along with demographic and baseline data. A listing of randomisation information by date and time of randomisation, randomisation number, participant ID, and treatment group assigned will be presented.

A listing of childbearing potential will be presented for female participants only.

Medical and surgical history will be summarised by system organ class (SOC) and preferred term (PT) according to MedDRA version 23.0 or later. HBV history including time since first HBV diagnosis (years), current anti-viral therapy, and duration of current anti-viral therapy (years) will be presented.

Time since first HBV diagnosis (years) and duration of current anti-viral therapy (years) will be calculated as: $[\text{date of informed consent} - \text{date of first diagnosis/start date of anti-viral therapy}]/365.25$.

Medical and surgical history and HBV history will be listed separately.

Usage of alcohol, recreational drugs, and tobacco categorised by current, past, and never used will be tabulated. Type of tobacco used will also be presented for the number and percentage of participants. The number of alcohol or type of tobacco units consumed and date of last drink, last drug use, and last use of each type of tobacco will be listed.

12.4 Prior and Concomitant Medications

Prior and concomitant medications, categorised by WHO drug dictionary preferred term (PT), will be summarised separately using the Intent-to-treat analysis set. The number and percentage of participants using each medication will be displayed together with the number and percentage of participants using at least one medication.

All prior and concomitant medications will be presented in a combined listing by participant.

12.5 Extent of Study Treatment Exposure

Exposure analyses will be summarised using the Safety analysis set.

The investigator records all injections of study vaccines or nivolumab given to the participant in the eCRF.

The number and percentage of participants who received both doses and the number and percentage of participants who received the first dose of the vaccine regimen only will be summarised.

Actual dose of nivolumab in mg/kg and mg will be derived using the planned dose, baseline weight (kg), and percentage of nivolumab infused. The reason study vaccine or nivolumab was not administered will be tabulated along with the reason not fully administered and percentage administered (if not fully administered) for nivolumab. This will be split by vaccination day.

The type of vaccine, administration date and time, vial lot #, location administered, percentage of vaccine administered, reason not administered, and if the participant was observed per protocol will be listed for study vaccination administration. For nivolumab administration, infusion date, start and stop time, planned dose (mg), actual dose given (mg/kg and mg), reason not administered, reason not fully administered, percentage administered, and if the participant was observed per protocol will be listed.

12.6 Immunogenicity Analyses

12.6.1 Secondary Endpoints

The secondary endpoints are:

- Magnitude and avidity of HBV specific CD4+ and CD8+ (ICS response, ELISpot)
- Effect on the frequency and magnitude of HBV infection markers (HBsAg, HBsAb seroconversion, Hepatitis DNA, HBeAg)

All HBV disease marker and immunogenicity results will be listed.

12.6.1.1 Reduction in HBsAg levels

Descriptive statistics including n, GM, GSD, median, minimum, maximum and 95% Exact confidence intervals (as defined in Section 10.4.1) for HBsAg will be summarised at Baseline, Day 7, Day 28, Day 35, Month 3, Month 6, and Month 9 and fold change from baseline to each visit as applicable. The number and percentage of participants with HBsAg loss of $> 0.5 \log_{10}$ and $> 1.0 \log_{10}$ from baseline at each visit will be presented. The denominator for the percentage will be the number of participants with non-missing values at the visit. This analysis will be presented using the Intent-to-treat analysis set, Per-protocol analysis set and Immunogenicity analysis set.

A repeated mixed measures model be used to assess HBsAg change from baseline at the scheduled time points (Day 7, Day 28, Day 35, Month 3, Month 6, and Month 9) using the Intent-to-treat analysis set. Least squares means, standard errors, 95% confidence intervals, and p-values will come from a repeated measures model on Change from baseline on the log scale (as defined in Section 10.2) with fixed factors for treatment group, time point, and treatment group * time point interaction, a covariate for \log_{10} baseline HBsAg, and a random effect for participant. An unstructured covariance matrix will be used to account for within-participant variability. This will be calculated using the SAS procedure proc mixed.

12.6.1.2 HBeAg Status

A summary of the number and percentage of participants with positive and negative baseline HBeAg status and HBeAg status at Month 9 will be presented using the Intent-to-treat analysis set.

12.6.1.3 Seroconversion Rate for HBeAg, HBeAb, HBsAg, and HBsAb

The number and percentage of participants meeting the criteria for HBeAg, HBeAb, HBsAg, and HBsAb seroconversion and sustained HBeAb positivity as defined in Section 10.4.2 will be presented at Month 9. The denominator for the percentage will be the number of participants fulfilling the baseline part of the seroconversion criteria (i.e. positive antigen or negative antibody at baseline, as applicable) with non-missing values at Month 9. This analysis will be presented using the Intent-to-treat analysis set.

12.6.1.4 Reduction in Hepatitis B DNA

The number and percentage of participants with No HBV DNA detected, < 20 IU/mL HBV DNA detected, and ≥ 20 IU/mL HBV DNA detected will be summarised at all planned time points (Baseline, Day 35, Month 3, Month 9). This analysis will be presented using the Intent-to-treat analysis set.

12.6.1.5 ICS response

These analyses will be presented using the Immunogenicity analysis set.

Background-subtracted overall cytokine response (%) as defined in Section 10.4.3 will be presented for each T cell (CD4+ and CD8+) and stimulation antigen (Core, Pol 1+2, Pol 3+4, Pre-S1/S2+S). Descriptive statistics including n, mean, standard deviation, median, minimum, maximum, and 95% CI for the median based on order statistics will be presented for absolute values, change from baseline, and fold change from baseline at all planned time points (Baseline, Day 7, Day 28, Day 35, Month 3, Month 6, Month 9).

DMSO overall cytokine response (%) will be presented similarly to background-subtracted overall cytokine response.

Graphical summaries using dot plots for the background-subtracted overall cytokine response (%) analysis above will be presented by planned time point separately for each T cell and stimulation antigen. The median overall cytokine response (%) per treatment group will be represented by a horizontal line. A dot plot will also be provided for DMSO overall cytokine response (%) results.

In addition, the median background-subtracted overall cytokine response for the stimulation antigens (Core, Pol 1+2, Pol 3+4, Pre-S1/S2+S) will be displayed altogether in a stacked bar plot for each treatment group by planned time point.

The 15 background-subtracted cytokine combinations (%) (see Table 4) and background-subtracted overall cytokine response (%) at Day 35 will be presented using polyfunctional profile plots separately for each T cell and stimulation antigen. Each of the cytokine combinations will be presented under the plot using Boolean values (+, -).

Also, for the background-subtracted overall cytokine response, to identify statistically significant differences between baseline and Day 35, a Wilcoxon signed-rank test using change from baseline will be performed within each of the four treatment groups for each T cell and stimulation antigen.

The median background-subtracted overall cytokine response for each T cell and stimulation antigen will be presented by all planned time points (Baseline, Day 7, Day 28, Day 35, Month 3, Month 6, Month 9) and p-values based on 2-sided Wilcoxon-Mann-Whitney (Wilcoxon rank sum) tests for pairwise comparisons between all treatment groups will also be presented. No adjustments will be made for the multiple comparisons.

All cytokine combinations (see Table 4) and overall response will be listed by T cell (CD4+ and CD8+), stimulation antigen, and time point. Only derived cytokine combinations will be included in this listing.

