9.0 Study Endpoints

9.1 Endpoints/Estimands

The below table links the endpoints to the study objectives.

Objectives	Endpoints/Estimands	Population
Primary		

Objectives	Endpoints/Estimands	Population

 • Determine the safety and reactogenicity of the following in participants with CHB infection and virally suppressed with oral antiviral medication: 
 – MVA-HBV vaccine – ChAdOx1-HBV plus MVA vaccines – ChAdOx1-HBV plus MVA vaccines and nivolumab 	
 • Safety and reactogenicity of the vaccine(s): incidence of adverse events (AEs), serious adverse events (SAEs), \geq Grade 3 study vaccine-related AEs within 4 weeks of vaccination • Safety of the vaccines with nivolumab: incidence of AEs, SAEs, \geq Grade 3 AEs within 4 weeks of dosing • Incidence of adverse events of special interest • Number and proportion of participants reporting treatment-emergent AEs within each treatment group • Number and proportion of participants within each treatment group with potentially clinically significant laboratory values and vital signs within each treatment group • Change from baseline in laboratory tests and vital sign measurements to each time point of collection 	Safety
Secondary 
 • Determine the immunogenicity of the following in participants with CHB infection and virally suppressed with oral antiviral medication: 
 – MVA-HBV vaccine – ChAdOx1-HBV plus MVA-HBV vaccines – ChAdOx1-HBV plus MVA-HBV vaccines administered with nivolumab • Determine the impact of PD-1 blockade timing relative to vaccination on immunogenicity in participants with CHB infection and virally suppressed with oral antiviral medication 	
 • Magnitude and avidity of HBV-specific CD4+ and CD8+ T cells induced by each regimen • Effect on the frequency and magnitude of HBV infection markers (HBsAg, Hepatitis B surface antibody seroconversion, hepatitis B DNA, HBeAg) 	
 • Immunogenicity (for ICS, ELISpot, and HBsAg analyses) • ITT (for HBsAg, HBeAg, HBV DNA, and seroconversion analyses)

Objectives	Endpoints/Estimands	Population

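### The between-group ICS tests leave out the pre-dose value, which costs power and can mislead when the groups differ widely at baseline; a baseline-adjusted rank test would use data already required

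*SAP*

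**What the plan says.** The secondary endpoint in SAP 9.1 is "Magnitude and avidity of HBV-specific CD4+ and CD8+ T cells induced by each regimen". SAP 12.6.1.5 serves it in three ways.

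- **Description.** Summary statistics "will be presented for absolute values, change from baseline, and fold change from baseline at all planned time points", by group.
- **Within-group test.** For Day 35 against baseline, "a Wilcoxon signed-rank test using change from baseline will be performed within each of the four treatment groups".
- **Between-group test.** The sentence opens "The median background-subtracted overall cytokine response for each T cell and stimulation antigen will be presented by all planned time points (Baseline" and goes on to list the six post-dose visits. It adds that "p-values based on 2-sided Wilcoxon-Mann-Whitney (Wilcoxon rank sum) tests for pairwise comparisons between all treatment groups will also be presented", followed by "No adjustments will be made for the multiple comparisons". It names no change score and no covariate.

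Two other places matter. SAP 9.2.5 admits a participant to the immunogenicity analysis set only with baseline data and at least one later ICS or ELISpot time point. SAP 12.6.1.1 analyses the change in HBsAg on the log scale "with fixed factors for treatment group, time point, and treatment group * time point interaction, a covariate for" log10 baseline HBsAg.

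**The concern.** The endpoint concerns what the regimen adds to the pre-dose response, but the between-group test compares the levels reached. Participants have chronic HBV infection and may carry some HBV-specific T cells before dosing. The background subtraction in SAP 10.4.3 removes the DMSO control, not that pre-dose response. A post-dose level therefore mixes what was there before with what was induced.

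These are the only between-group T-cell tests that the SAP explicitly plans; ELISpot (12.6.1.6) has none. They therefore carry the T-cell side of the PD-1 timing objective. The relevant contrast is Group 3 against Group 4, and Group 4 closed at 9 participants.

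Baseline gaps need not come from chance alone. Under SAP 8.2 at least 6 participants went straight into Group 1, and then at least 6 straight into Group 2, before Groups 3 and 4 opened. Comparisons involving Group 1 or 2 are therefore only partly concurrent.

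**Working it through.** **1. The plan's own figure.** The only probability given with the sample size (SAP 8.1) is an 80% chance of seeing an adverse event of 10% incidence among 16 participants: 1 − 0.9^16 = 0.815, so it reproduces. It is a safety figure. The documents give no power, SD, effect size or correlation for ICS.

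**2. Which variable is tested.** The SAP does not call it absolute in this sentence. The reading follows from the named variable and from the inclusion of Baseline: change at Baseline is zero for everyone, so a test there can only be on the level. The SAP also says so where it does use baseline, in the signed-rank test and the HBsAg model.

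**3. Number of tests.** 6 pairs × 2 T-cell types × 4 antigens × 7 visits = 336, of which 6 × 2 × 4 = 48 are at Baseline and 288 are post-dose.

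**4. Chance imbalance.** In units of the between-participant SD, the difference in baseline means has SD √(1/n1 + 1/n2). Group sizes are from SAP 8.1: Group 1 has 10, Group 4 has 9, and 16 are planned for Groups 2 and 3. The tail probabilities are two-sided normal; for 10 v 9, for example, 0.5/0.459 = 1.09 and 1/0.459 = 2.18.

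| Comparison | SD of gap | Gap ≥ 0.5 SD | Gap ≥ 1 SD |
|---|---|---|---|
| 16 v 16 | 0.35 | 16% | 0.5% |
| 10 v 16 | 0.40 | 21% | 1.3% |
| 9 v 16 | 0.42 | 23% | 1.6% |
| 10 v 9 | 0.46 | 28% | 3% |

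**5. Simulation.** The assumptions are not in the documents: normal scores, SD 1 at both visits, baseline to post-dose correlation 0.3 to 0.9, a shift of 0 or 1 SD, two-sided 5% level, 10,000 runs per setting. The tests compared are the rank-sum on the level (as planned), the rank-sum on change, and a Quade-type baseline-adjusted rank test.

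*No effect, averaged over random allocation* (16 v 16, 10 v 16, 9 v 16): rejection is 0.042–0.048 as planned and 0.046–0.052 adjusted.

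*No effect, given an observed baseline gap of 1 SD, 16 v 16:*

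| Correlation | As planned | Change | Adjusted |
|---|---|---|---|
| 0.3 | 0.110 | 0.307 | 0.026 |
| 0.5 | 0.226 | 0.232 | 0.033 |
| 0.7 | 0.443 | 0.158 | 0.034 |
| 0.9 | 0.773 | 0.086 | 0.039 |

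With a gap of 0.5 SD, the planned test rejects in only 0.057–0.082.

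*True shift of 1 SD (power):*

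| Sizes | Correlation | As planned | Change | Adjusted |
|---|---|---|---|---|
| 16 v 16 | 0.3 | 0.753 | 0.602 | 0.784 |
| 16 v 16 | 0.5 | 0.746 | 0.751 | 0.844 |
| 16 v 16 | 0.7 | 0.743 | 0.926 | 0.933 |
| 9 v 16 | 0.3 | 0.582 | 0.448 | 0.631 |
| 9 v 16 | 0.5 | 0.573 | 0.585 | 0.697 |
| 9 v 16 | 0.7 | 0.580 | 0.807 | 0.833 |

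A separate run of 4,000 per setting gave 75% against 78%, 84% and 94% at 16 v 16, and 57% against 61%, 69% and 83% at 16 v 9. Hence about 62% for the adjusted test at 16 v 9 and correlation 0.3.

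**6. Values at zero.** SAP 10.4.3 sets negative background-subtracted values to zero, so ties are likely. Further simulations (3,000 runs per setting) assumed a share of values at zero before any effect.

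- Skewed data, 50% at zero, correlations 0.3, 0.5 and 0.7: 72–74% as planned against 75%, 80% and 90% adjusted at 16 v 16; 56–58% against 59%, 65% and 76% at 16 v 9. Null rejection was 4–6% for both tests.
- 70% at zero, 16 v 16: 67% against 69%, 73% and 82%.
- At zero correlation there was no gain.

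**The case against.** The strongest reply is that the planned tests are valid. A reader might infer from the missing baseline term that pre-existing responses and chance imbalance are routinely counted as regimen effects. The documents and the arithmetic do not support that. Under randomisation, chance imbalance is already part of the rank-sum null distribution, and simulated type I error is 4–5%. A 0.5-SD gap changes little, and a 1-SD gap is uncommon by chance. This stands.

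A reader might also infer that these are the only planned between-group immunogenicity tests. They are not. SAP 9.2.2 counts HBsAg among the immunogenicity analyses, and the 12.6.1.1 model compares groups over time, reports p-values and already adjusts for baseline. The statement holds only for T-cell assays. This stands too.

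Third, baseline-referenced evidence is planned: change and fold change by group, and the within-group test. True, but neither these summaries nor the Baseline p-values correct a post-dose between-group p-value.

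Fourth, the stakes are limited. Protocol 10.2.2.1 describes most of the analysis as descriptive, Protocol 4.1 rests the participant number on feasibility, and no decision rule hangs on these p-values. That limits the priority of the point but gives no reason to leave a required measurement unused.

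Finally, the size of the gain depends on a correlation that nobody has stated. Protocol 1.5 says chronically infected patients do not mount a sufficiently robust cellular response, so baseline values may be low and predict little. This is fair, and is why a range is shown.

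**Conclusion.** The planned between-group ICS tests answer a slightly different question from the endpoint and are less efficient than they need be. Average type I error is not at fault. The cost is power: at 16 v 16, about 75% against about 78%, 84% and 93% with adjustment; at 16 v 9, about 58% against 62%, 70% and 83%. These figures assume a 1-SD effect, normal scores and correlations of 0.3, 0.5 and 0.7. The gain is about 2–5 points at 0.3 and about 15–25 points at 0.7, smaller with many zeros, and nil at zero correlation.

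The second cost is conditional. If a 1-SD baseline gap is seen and there is no effect, the planned 16 v 16 test is positive in 11% to 77% of trials (correlation 0.3 to 0.9), against 3% to 4% after adjustment. The staged opening of the groups adds a source of imbalance beyond chance. Baseline adjustment reduces that but does not fully correct it. The immunogenicity set is drawn from the per-protocol set, so actual numbers may be smaller than those used here.

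**What to change.** In SAP 12.6.1.5, replace the rank-sum tests at the six post-baseline visits with a baseline-adjusted rank test, for example Quade rank ANCOVA. Within each pair of groups, T-cell type and antigen, rank the post-dose and baseline values (mid-ranks for ties), regress the first ranks on the second, and compare the residuals between groups.

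Do not simply test change scores. At correlation 0.3 their power at 16 v 16 is 60%, below the 75% of the planned test, and they over-correct when a baseline gap is present.

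Keep the change and fold-change summaries. The 48 Baseline tests may be dropped, or kept and labelled descriptive. Add a sentence that comparisons involving Groups 1 and 2 include participants allocated before Groups 3 and 4 opened, and that adjustment does not fully remove this.

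The cost is SAP wording and a few lines of SAS. No new data are needed, and the analysis set already requires baseline data. If the SAP can no longer be amended before database lock, document the added analysis in the study report, as Protocol 10.2 requires.

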12.6.1.6 ELISpot response

These analyses will be presented using the Immunogenicity analysis set.

Average background-subtracted antigen specific IFN γ ELISpot response (SFU/10⁶ PBMC) will be presented for each stimulation antigen (Core, Pol1, Pol2, Pol3, Pol4, Pre-S, S, Total, and Total (adjusted) [as defined in Section 10.4.4]). Descriptive statistics including n, mean, standard deviation, median, minimum, maximum, and 95% CI for the median based on order statistics will be presented for absolute values, change from baseline, and fold change from baseline at all planned time points (Baseline, Day 7, Day 28, Day 35, Month 3, Month 6, Month 9).

Also, for the average background-subtracted antigen specific IFN γ ELISpot response, to identify statistically significant differences between baseline and Day 35, a Wilcoxon signed-rank test using change from baseline will be performed within each of the four treatment groups for each stimulation antigen.

Similar to the graphical summaries described for the ICS analysis, for average background-subtracted antigen specific IFN γ ELISpot response (SFU/10⁶ PBMC) a dot plot will be presented by planned time point separately for each stimulation antigen (Core, Pol1, Pol2, Pol3, Pol4, Pre-S, S, Total, Total adjusted).

A stacked bar chart will also be displayed for the median total (pooled over antigens) response (SFU/10⁶ PBMC) by treatment group and planned time point.

In addition, a line plot of mean \pm SD of the total (pooled over antigens) response (SFU/10⁶ PBMC) for each treatment will be displayed by planned time point.

A summary of the number and percentage of participants who meet the total (pooled over antigens) responder criteria as defined in Section 10.4.4 will be presented at all planned time points.

The average (from samples run in triplicate), background-subtracted antigen-specific IFN γ ELISpot response (SFU/10⁶ PBMC) will be listed by stimulation antigen (Core, Pol1, Pol2, Pol3, Pol4, Pre-S, S, Total) for each participant at each time point.

